## 5.2 Exclusion criteria

Participants meeting any of the following criteria are not eligible for inclusion in this study. No additional exclusions may be applied by the investigator, in order to ensure that the study population will be representative of all eligible participants.

1. Participants with radiographic evidence for sacroiliitis, grade  $\geq 2$  bilaterally or grade  $\geq 3$  unilaterally (radiological criterion according to the modified New York diagnostic criteria for AS) as assessed by central reader
2. Inability or unwillingness to undergo MRI scan (e.g., participants with pacemakers, aneurysm clips or metal fragments / foreign objects in the eyes, skin or body that are not MRI compatible)
3. Chest X-ray or computed tomography (CT) scan with evidence of ongoing infectious or malignant process, obtained within 3 months of screening and evaluated by a qualified physician
4. Participants taking high potency opioid analgesics (e.g., methadone, hydromorphone, morphine)
5. Previous exposure to secukinumab or any other biologic drug directly targeting IL-17 or IL-17 receptor
6. Use of any investigational drug and/or devices within 4 weeks of randomization, or a period of 5 half-lives of the investigational drug, whichever is longer
7. History of hypersensitivity to the study drug or its excipients or to drugs of similar chemical classes
8. Any therapy by intra-articular injections (e.g., corticosteroid) within 4 weeks before randomization
9. Any intramuscular corticosteroid injection within 2 weeks before randomization
10. Participants previously treated with any biological immunomodulating agents, except those targeting TNF $\alpha$
11. Participants who have taken more than one anti-TNF $\alpha$  agent

12. Previous treatment with any cell-depleting therapies including but not limited to anti-CD20 or investigational agents (e.g., anti-CD52, anti-CD4, anti-CD5, anti-CD3, anti-CD19)
13. Pregnant or nursing (lactating) women, where pregnancy is defined as the state of a female after conception and until the termination of gestation, confirmed by a positive human chorionic gonadotropin (hCG) laboratory test
14. Women of child-bearing potential, defined as all women physiologically capable of becoming pregnant, **unless** they are using effective methods of contraception during entire study or longer if required by locally approved prescribing information Effective contraception methods include:
  - Total abstinence, when this is in line with the preferred and usual lifestyle of the participant. Periodic abstinence (e.g., calendar, ovulation, symptothermal, post-ovulation methods) and withdrawal are not acceptable methods of contraception
  - Female sterilization (have had surgical bilateral oophorectomy with or without hysterectomy), total hysterectomy, or tubal ligation at least six weeks before taking study treatment. In case of oophorectomy alone, only when the reproductive status of the woman has been confirmed by follow up hormone level assessment
  - Male sterilization (at least 6 months prior to screening). For female participants on the study, the vasectomized male partner should be the sole partner for that participant
  - Barrier methods of contraception: Condom or Occlusive cap (diaphragm or cervical/vault caps) with spermicidal foam/gel/film/cream/vaginal suppository
  - Use of oral, injected or implanted hormonal methods of contraception or other forms of hormonal contraception that have comparable efficacy (failure rate <1%), for example hormone vaginal ring or transdermal hormone contraception or placement of an intrauterine device (IUD) or intrauterine system (IUS)

In case of use of oral contraception, women should have been stable on the same pill for a minimum of 3 months before taking study treatment.

Women are considered post-menopausal and not of child bearing potential if they have had 12 months of natural (spontaneous) amenorrhea with an appropriate clinical profile (e.g., age appropriate, history of vasomotor symptoms) or have had surgical bilateral oophorectomy (with or without hysterectomy), total hysterectomy or tubal ligation at least six weeks ago. In the case of oophorectomy alone, only when the reproductive status of the woman has been confirmed by follow up hormone level assessment is she considered not of childbearing potential.

If local regulations deviate from the contraception methods listed above to prevent pregnancy, local regulations apply and will be described in the informed consent form (ICF).

15. Active ongoing inflammatory diseases other than nr-axSpA that might confound the evaluation of the benefit of secukinumab therapy, including inflammatory bowel disease or uveitis
16. Underlying metabolic, hematologic, renal, hepatic, pulmonary, neurologic, endocrine, cardiac, infectious or gastrointestinal conditions, which in the opinion of the investigator immunocompromises the participant and/or places the participant at unacceptable risk for participation in an immunomodulatory therapy

17. Significant medical problems or diseases, including but not limited to the following:  
uncontrolled hypertension ( $\geq 160/95$  mmHg), congestive heart failure (New York Heart Association status of class III or IV), uncontrolled diabetes, or very poor functional status unable to perform self-care
18. History of clinically significant liver disease or liver injury as indicated by abnormal liver function tests such as Serum Glutamic Oxaloacetic Transaminase (SGOT) (Aspartate Aminotransferase (AST)), SGPT (Alanine Aminotransferase (ALT)), alkaline phosphatase, or serum bilirubin. The Investigator should be guided by the following criteria:
  - Any single parameter may not exceed 2 x ULN. A single parameter elevated up to and including 2 x ULN should be re-checked once more as soon as possible, and in all cases, at least prior to enrollment/randomization, to rule out lab error.
  - If the total bilirubin concentration is increased above 2 x ULN, total bilirubin should be differentiated into the direct and indirect reacting bilirubin.
19. History of renal trauma, glomerulonephritis, or participants with one kidney only, or a serum creatinine level exceeding 1.5 mg/dL (132.6  $\mu$ mol/L)
20. Screening total White blood cell(s) (WBC) count  $<3,000/\mu\text{L}$ , or platelets  $<100,000/\mu\text{L}$  or neutrophils  $<1,500/\mu\text{L}$  or hemoglobin  $<8.5$  g/dL (85 g/L)
21. Active systemic infections during the last two weeks prior to randomization (exception: common cold)
22. History of ongoing, chronic or recurrent infectious disease or evidence of tuberculosis infection as defined by either a positive purified protein derivative (PPD) skin test (the size of induration will be measured after 48-72 hours, and a positive result is defined as an induration of  $\geq 5$  mm or according to local practice/guidelines) or a positive QuantiFERON TB-Gold test as indicated in the assessment schedule in [Table 8-1](#). Participants with a positive test may participate in the study if further work up (according to local practice/guidelines) establishes conclusively that the participant has no evidence of active tuberculosis. If presence of latent tuberculosis is established, then treatment according to local country guidelines must have been initiated
23. Known infection with HIV, hepatitis B or hepatitis C at screening or randomization
24. History of lymphoproliferative disease or any known malignancy or history of malignancy of any organ system within the past 5 years (except for basal cell carcinoma or actinic keratoses that have been treated with no evidence of recurrence in the past 3 months, carcinoma in situ of the cervix or non-invasive malignant colon polyps that have been removed)
25. Current severe progressive or uncontrolled disease which in the judgment of the clinical investigator renders the participant unsuitable for the trial
26. Inability or unwillingness to undergo repeated venipuncture (e.g., because of poor tolerability or lack of access to veins)
27. Inability or unwillingness to receive subcutaneous injections with PFS
28. Any medical or psychiatric condition which, in the investigator's opinion, would preclude the participant from adhering to the protocol or completing the study per protocol
29. Donation or loss of 400 mL or more of blood within 8 weeks before dosing

30. History or evidence of ongoing alcohol or drug abuse, within the last six months before randomization
31. Plans for administration of live vaccines during the study period or 6 weeks prior to randomization

## 6 Treatment

### 6.1 Study treatment

Novartis Global Clinical Supply will supply the following study treatments:

- Investigational Treatment:
  - Secukinumab 150 mg provided in a 1 mL PFS (one PFS for 150 mg dose)
- Reference Therapy:
  - Secukinumab placebo (Placebo) provided in a 1 mL PFS

At Week 16, all participants will switch to open label secukinumab 150 mg, including all placebo participants; however, all participants, investigators and site staff will remain blinded to the original randomized treatment group assignment (150 mg vs placebo) until the end of the trial.

At Week 24, non-responders (defined as not achieving ASAS20) will be escalated to secukinumab 300 mg (two PFS for 150 mg dose). Responders will continue secukinumab 150 mg treatment.

#### 6.1.1 Investigational and control drugs

**Table 6-1      Investigational and control drug**

Investigational/ Control Drug (Name and Strength)	Pharmaceutical Dosage Form	Route of Administration	Supply Type	Sponsor (global or local)
Secukinumab 150 mg	PFS	subcutaneous injection	Double Blind Supply	Sponsor (global)
Secukinumab 150 mg	PFS	subcutaneous injection	Open label	Sponsor (global)
Secukinumab placebo	PFS	subcutaneous injection	Double Blind Supply	Sponsor (global)

In the double blind period, the Secukinumab/Placebo PFSs are packaged in a double-blinded fashion to meet dosing requirements until including Week 12 dispensing, thereafter at Week 16 and onwards open label treatment will start.

In the open label period (starting at Week 16), the study medication will be provided in open label fashion for the 150 mg and from Week 24 onwards for the 300 mg doses. Open label medications will be supplied until the last dose is given at Week 48.

The double blind period medication will be labeled as follows:

- Double-blind Secukinumab and Placebo PFS will be labeled as AIN457 150mg/1mL/Placebo.

The open label period study medication will be labeled as follows:

- Open label Secukinumab PFS will be labeled as AIN457 150mg/1mL

For detailed instructions on storage of the investigational treatments, please refer to medication label.

### **6.1.2 Additional study treatments**

Not Applicable

### **6.1.3 Treatment arms/group**

#### **Double Blind Period (Treatment Period 1)**

Participants in double-blind period will be assigned to one of the following two treatment groups in a ratio of 1:1. Participants will receive study treatment at BSL, Weeks 1, 2, 3, and 4, followed by treatment every 4 weeks through Week 12.

- Group 1: secukinumab 150 mg (1 mL, 150 mg/mL) s.c. PFS at BSL, Weeks 1, 2, and 3, followed by administration every 4 weeks starting at Week 4.
- Group 2: placebo (1 mL) s.c. PFS at BSL, Weeks 1, 2 and 3, followed by administration every 4 weeks starting at Week 4.

#### **Open Label Period (Treatment Period 2 and 3)**

**Treatment Period 2:** At Week 16, Group 1 participants will continue using secukinumab 150 mg and Group 2 participants will start receiving secukinumab 150 mg dosing every four weeks. Treatment will be provided open label from Week 16 onward, as all participants will be taking 150 mg s.c. every 4 weeks. However, all participants and investigators/site staff will remain blinded to the original randomized treatment group assignment (150 mg vs placebo).

**Treatment Period 3:** At Week 24, participants in open label period will be assessed as being Open Label Period Responder or Open Label Period non-responder and will receive the study treatment every 4 weeks through Week 48 as follows.

- **Open Label Period Responder:** Secukinumab 150 mg provided in a 1 mL PFS (**one** PFS for 150 mg dose, s.c.), administration every 4 weeks starting at Week 24.
- **Open Label Period non-responder:** Secukinumab 150 mg provided in a 1 mL PFS (**two** PFS for 300 mg dose, s.c.), administration every 4 weeks starting at Week 24.

### **6.1.4 Treatment duration**

The planned study duration is 60 weeks with the last secukinumab treatment administration at Week 48. Participants may be discontinued from treatment earlier due to unacceptable toxicity, disease progression and/or if the treatment is discontinued at the discretion of the investigator or the participant. For participants who in the opinion of the investigator are still deriving clinical benefit from the study drug, every effort will be made to continue provision of study treatment.

Participants should continue to receive the study treatment until one or more criteria for treatment discontinuation described in [Section 9.1.1](#) are met.

## 6.2 Other treatments

### 6.2.1 Concomitant therapy

During this study, NSAIDs, selected analgesics, selected disease-modifying anti-rheumatic drugs (DMARDs), i.e. MTX and sulfasalazine, and systemic corticosteroids are permitted as part of participants' routine medical care and will not be provided by Novartis. The investigational site and / or the participant's treating physician are responsible for prescribing and providing any background therapy.

The investigator should instruct the participant to notify the study site about any new medications he/she takes after the participant was enrolled into the study. All medications, procedures and significant non-drug therapies (including physical therapy and blood transfusions) administered after the participant was enrolled into the study must be recorded in the Prior/Concomitant medications electronical case report form (eCRF) page.

#### 6.2.1.1 Permitted concomitant therapy requiring caution and/or action

**Guidelines for the use of specific medications are provided below:**

##### **Methotrexate**

Participants taking MTX ( $\leq 25$  mg/week) must be on a stable dose for at least 4 weeks before randomization and maintained stable until Week 24. Any changes in dose or initiation after Week 24 must be recorded in the Prior/Concomitant medications eCRF page.

##### **Folic acid**

Participants on MTX must be taking folic acid supplementation before randomization and during the trial to minimize the likelihood of MTX associated toxicity.

##### **Sulfasalazine**

Participants taking sulfasalazine ( $\leq 3$  g/day) must be on a stable dose for at least 4 weeks before randomization and maintained stable until Week 24. Any changes in dose or initiation after Week 24 must be recorded in the Prior/Concomitant medications eCRF page.

##### **Leflunomide wash-out with cholestyramine**

In case of leflunomide treatment, a drug wash-out of 8 weeks has to be performed. However, another wash-out procedure might be considered. Cholestyramine could be given orally to wash-out the drug at a dose of 8 g three times a day (t.i.d.) Cholestyramine reduced plasma levels of the active leflunomide metabolite by approximately 40% in 24 hours and by 49 % to 65 % in 48 hours in three healthy volunteers. The administration of cholestyramine is recommended in participants who require a drug elimination procedure. If a participant receives the dose of 8 g t.i.d. for 11 days, he/she could be safely randomized 4 weeks after the beginning of the 11 days treatment period.

After all Week 24 assessments are completed, leflunomide therapy may be initiated as a background medication. Any initiation or changes in dose after Week 24 must be recorded in the Prior/Concomitant medications eCRF page.

##### **Systemic corticosteroids**

Treatment with systemic corticosteroids is permitted if the dose was stable within the 2 weeks preceding randomization, up to a maximum daily dosage of 10 mg prednisone equivalent. After Week 24, the dose and regimen of systemic corticosteroids may be modified as per investigator's judgment and participant's needs, although the corticosteroid dose should not be reduced rapidly. Any change in the dose of systemic corticosteroids during the trial must be recorded on the corresponding eCRF page.

Intra-articular corticosteroids are not permitted within the 4 weeks preceding randomization and up to Week 24. No single injection should exceed 40 mg of triamcinolone (or equivalent) and the total dose of intra-articular corticosteroid may not exceed 80 mg of triamcinolone (or equivalent) during any 52-week period.

Any change in the dose of systemic corticosteroids, or any corticosteroid injections during the trial must be recorded in the Prior/Concomitant medications on the corresponding eCRF page.

#### **NSAIDs including COX-1 or COX-2 inhibitors and acetaminophen/paracetamol**

Participants on regular use of non-steroidal anti-inflammatory drugs (NSAIDs) or paracetamol/acetaminophen should be on stable dose for at least 2 weeks before randomization to allow inclusion in the study.

NSAIDs, low strength opioids or paracetamol/acetaminophen PRN (Pro re nata) can be taken during the study; however, participants should refrain from any intake during at least the 24 hours before a visit with disease activity assessment.

After the Week 24 assessments are completed, a change in the NSAID intake regimen is permitted.

#### **TNF $\alpha$ inhibitors**

If TNF $\alpha$  inhibitors are chosen as escape treatment for participants considered as inadequate responders from Week 28, a wash out period has to be considered after administration of the last dose of study treatment for safety reasons. Initiation of TNF $\alpha$  inhibitors must be recorded on the corresponding eCRF page.

TNF $\alpha$  inhibitors prescribed in accordance with investigator practice, treatment guidelines or locally approved uses will be considered standard of care and will not be supplied by the sponsor.

#### **6.2.2 Prohibited medication**

Use of the treatments displayed in [Table 6-2](#) is NOT allowed after the start of the washout period unless otherwise specified below. Treatment continuation with secukinumab at the end of the treatment phase is acceptable.

Live vaccines should not be given during the study period or 6 weeks prior to randomization and until 12 weeks after last study treatment administration (follow up visit).

**Table 6-2      Prohibited medication**

Medication	Prohibition period	Action taken
Etanercept or "Yi Sai Pu", "An Bai Nuo" and "Qiang Ke"	4 weeks washout period prior to randomization to until Week 28	Delay randomization or discontinue from study treatment

Medication	Prohibition period	Action taken
Infliximab	8 weeks washout period prior to randomization to until Week 28	Delay randomization or discontinue from study treatment
Adalimumab, golimumab, certolizumab	10 weeks washout period prior to randomization to until Week 28	Delay randomization or discontinue from study treatment
Unstable dose of MTX or sulfasalazine	4 weeks prior to randomization to until Week 24	Achieve stable dose for at least 4 weeks prior to randomization and remain on a stable dose up to Week 24
Other DMARD (except MTX or sulfasalazine)	4 weeks washout period prior to randomization to until Week 24,	Delay randomization or discontinue from study treatment
Leflunomide	8 weeks washout period prior to randomization to until Week 24	Delay randomization or discontinue from study treatment
Leflunomide with Cholestyramine washout	4 weeks washout period prior to randomization to until Week 24	Delay randomization or discontinue from study treatment
Unstable dose of NSAIDs (COX1 or COX2 inhibitors)	2 weeks prior to randomization to until Week 24	Achieve stable dose for at least 2 weeks prior to randomization and remain on a stable dose up to Week 24
Systemic corticosteroids > 10 mg prednisone equivalent*	2 weeks prior to randomization to until Week 24	Achieve stable dose for at least 2 weeks prior to randomization and remain on a stable dose up to Week 24
Intra-articular steroid injections	4 weeks prior to randomization to until Week 24	Delay randomization or discontinue from study treatment
Any biological immunomodulating agents, except those targeting TNF $\alpha$ **	From screening to follow up visit	No prior exposure allowed
Any cell-depleting therapies including but not limited to anti-CD20 or investigational agents (e.g., anti-CD52, anti-CD4, anti-CD5, anti-CD3, anti-CD19)	From screening to follow up visit	No prior exposure allowed
Any investigational treatment or participation in any interventional trial	4 weeks or 5 half-lives (whichever is longer) prior to randomization to follow up visit	Delay randomization or discontinue from study treatment
Analgesics other than paracetamol/acetaminophen or low strength opioids PRN(Pro re nata)	4 weeks prior to randomization to follow up visit	Delay randomization or discontinue from study treatment
Live vaccinations	6 weeks prior to randomization to follow up visit	Delay randomization or discontinue from study treatment
Traditional Chinese Medicines***	Until Week 24, if adjustment needed by investigator's judgement	Delay randomization or discontinue from study treatment

\*See details about corticosteroid management in [Section 6.2.1](#).

\*\*These agents fall under the category of biologic immunomodulators and are prohibited medications.

Administration of these agents requires study treatment discontinuation (see [Section 9.1](#))

\*\*\*Traditional Chinese herb medicines, Chinese patent medicines etc.

### 6.2.3 Escape Medication

Escape medication is defined as any new therapeutic intervention or a significant change to ongoing therapy made because a participant is experiencing either no benefit from participation in the trial or worsening/exacerbation of their disease.

From Week 28 on, based on the clinical judgment of disease activity by the investigator and the participant, participants may be considered as inadequate responders. Participants who are repeatedly (e.g. two or more consecutive visits) considered to be inadequate responders will have the option to enter escape. Upon entering “escape”, participants can be switched to treatment according to locally applicable clinical practice.

Participants have the option to either discontinue study treatment (escape to locally applicable clinical practice treatment but continue study participation) or completely discontinue from the study (no further study participation) for any reason.

While all participants have already switched to open label treatment with secukinumab 150 mg at Week 16, the originally randomized treatment assignment before Week 16 (secukinumab 150 mg or placebo) will remain blinded until the end of study. From Week 24 onward, if based on the clinical practice, the participants escape to include the use of a biologic such as a TNF $\alpha$  inhibitor, it should be prescribed in accordance with investigator practice and local treatment guidelines. Participants switching to a biologic therapy (e.g. anti-TNF $\alpha$ ) other than secukinumab must not receive any further study medication and the investigator will be recommended to consider a wash out period after the last administration of study treatment prior to starting any other biologic treatment. All other participants will continue their original assigned treatment.

Any use of escape medication must be recorded in the Prior/Concomitant medications eCRF.

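### Protocol Section 6.2.3 dates escape to a TNF inhibitor from Week 24 in one paragraph, while its own second paragraph, Section 6.2.1.1 and Table 6-2 give Week 28.

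*Protocol*

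**What the plan says.** Section 6.2.3 of the protocol opens escape in its second paragraph: "From Week 28 on, based on the clinical judgment of disease activity by the investigator and the participant, participants may be considered as inadequate responders". It then adds a condition: "Participants who are repeatedly (e.g. two or more consecutive visits) considered to be inadequate responders will have the option to enter escape". Two paragraphs later the same section dates escape to a biologic earlier: "From Week 24 onward, if based on the clinical practice, the participants escape to include the use of a biologic such as a" TNF inhibitor. That sentence goes on to say that the biologic is to be prescribed under investigator practice and local guidelines.

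The TNF inhibitor entry in Section 6.2.1.1 covers these drugs when "chosen as escape treatment for participants considered as inadequate responders from Week 28". Table 6-2 lists them as prohibited in three rows: "4 weeks washout period prior to randomization to until Week 28" for etanercept and its local equivalents, "8 weeks washout period prior to randomization to until Week 28" for infliximab, and "10 weeks washout period prior to randomization to until Week 28" for adalimumab, golimumab and certolizumab. For all three rows, the action after randomization is to discontinue study treatment.

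Section 6.6 bars new interventions only until the Week 24 assessments are done. It then names NSAIDs and DMARDs as changeable background medication and gives no start week for biologics. Section 6.5.1 moves ASAS20 non-responders to 300 mg at the Week 24 visit.

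**The concern.** A site that follows the fourth paragraph of Section 6.2.3 could start a TNF inhibitor at Week 24 as escape. A site that follows Table 6-2 would have to treat the same act as use of prohibited medication. These are operative instructions, and nothing in the protocol ranks one above the other.

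Two things are at stake. The first is classification: SAP Section 2.3.1 tabulates participants with each protocol deviation, and the same event could be counted or not according to the passage applied. The second is the make-up of the 300 mg group. Section 1.2 makes assessment of 300 mg in Week 24 non-responders a stated purpose, and SAP Section 2.1.1.1 reports treatment sequences ending in 300 mg and a pooled group with any 300 mg exposure. A non-responder who switches at Week 24 would not enter those groups. One who switches at Week 28 after an escalated dose would.

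**Working it through.** The plan states no figure on this point, so there is none to reproduce. The check sets the passages side by side and then counts scheduled doses.

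**1. Dates given for a TNF inhibitor or other biologic**

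| Place in protocol | Week | What the week governs |
|---|---|---|
| 6.2.3, fourth paragraph | 24 | Escape that includes a biologic |
| 6.2.3, second paragraph | 28 | Judgement as inadequate responder, which leads to escape |
| 6.2.1.1, TNF inhibitors | 28 | TNF inhibitor chosen as escape |
| Table 6-2, etanercept row | 28 | End of prohibition |
| Table 6-2, infliximab row | 28 | End of prohibition |
| Table 6-2, adalimumab, golimumab and certolizumab row | 28 | End of prohibition |
| 6.6 | 24 | End of the general bar on new interventions; no week for biologics |

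Section 6.6 does not settle the matter. It lifts a general bar at Week 24, but it also refers back to Section 6.2.2, where the specific prohibition runs to Week 28.

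**2. Length of the conflict**

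Week 28 − Week 24 = 4 weeks. Dosing is every 4 weeks (Section 6.1.3), so this is one dosing interval.

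**3. Doses before the earliest permitted switch**

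Scheduled doses from Week 24 through Week 48: (48 − 24) / 4 + 1 = 7. Section 6.2.3 ends study drug once another biologic is taken up, so the doses received are those scheduled before the switch week.

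- Escape opening at Week 24: 0 of 7.
- Escape opening at Week 28: 1 of 7, the Week 24 dose.

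For an ASAS20 non-responder, that single dose is the first 300 mg dose. The two readings therefore differ by whether such a participant, switching as early as allowed, has had any 300 mg at all.

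**4. What does not change**

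The primary endpoint and all secondary efficacy endpoints are at Week 16 (Table 2-1). The window opens 24 − 16 = 8 weeks later. Under Sections 6.2.3 and 6.6 and Table 6-2, a participant who takes up another biologic in this window stops study drug.

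**5. Number affected**

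The documents give neither an expected Week 24 non-response rate nor an expected rate of switching to a biologic. The group at issue is smaller than all Week 24 non-responders: only those for whom a TNF inhibitor is wanted inside the 4-week window. No count can be stated.

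**The case against.** The strongest reply is that the Week 24 sentence is conditional. It describes how a biologic is to be prescribed once a participant escapes and is not itself an entry rule. Entry is set in the second paragraph, repeated in Section 6.2.1.1 and backed by three table rows. On this view it is a stray date in one clause. This has force, and it limits the weight of the point. It does not remove the point, because the sentence still attaches a week to biologic escape and nothing in Section 6.2.3 makes it subject to the other date. One could also suppose that the decision is taken at Week 24 and the drug started at Week 28 after a wash-out, but no passage says so.

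Three stronger readings are tempting and are not supported.

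- A reader might infer a third conflicting date from the consecutive-visit condition: visits at Weeks 28 and 32, escape at Week 32, and so 32 − 24 = 8 weeks of conflict. The condition is offered as an example, does not say whether visits before Week 28 count, and is compatible with Week 28. Week 32 is an assumption.
- A reader might infer that the passage followed decides who stays on study drug. Section 6.2.3 lets participants stop study treatment for any reason, Section 9.1.1 lists participant decision, and Section 6.5.1 directs non-responders to 300 mg whichever date applies to escape. A non-responder can leave before any 300 mg dose under either date.
- A reader might infer a safety conflict over a second biologic. Sections 6.2.1.1 and 6.2.3 both ask that a wash-out be considered, and the two start weeks do not create a contradiction between them on that.

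**Conclusion.** The contradiction is real and current: Week 24 in one paragraph of Section 6.2.3, against Week 28 in another paragraph of that section, in Section 6.2.1.1 and in Table 6-2. It spans 4 weeks and at most one scheduled dose for a participant who switches as early as allowed. Its firm consequence is that TNF inhibitor use in Weeks 24 to 28 can be labelled either escape or prohibited medication. Its possible consequence is a difference in who has 300 mg exposure before switching, to an extent the documents do not allow to be quantified. The dose count assumes the 4-weekly schedule is kept and that no dose is given at the visit where the switch occurs.

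This is an inconsistency that should be corrected. It is not a flaw in the trial's main comparison, since the Week 16 analyses are unaffected and the 300 mg phase is open-label and not randomized. The effect on efficacy summaries after Week 24 cannot be judged, because the relevant SAP section is not visible in the public text.

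**What to change.** Reconcile Sections 6.2.1.1 and 6.2.3 and Table 6-2 so that one start week for escape to a biologic appears in all three. In the same place, state whether inadequate-response visits before that week count toward the condition of two or more consecutive visits. The choice of week is a clinical matter for the sponsor.

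The cost is a wording change in three places, with no effect on the primary analysis or sample size. SAP Amendment 2 was written shortly before the Week 52 database lock. For participants already past Week 28, the clarification would therefore serve mainly to fix how such use is classified, and it should be settled before the deviation tables are produced.

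A flag in the SAP for biologics started in Weeks 24 to 28 is optional. The planned disposition, deviation and concomitant-therapy tables (SAP Sections 2.3.1 and 2.4.2) already carry most of the information. The flag would also miss a participant who stopped study drug at Week 24 and began the biologic only after the window had closed.
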